### **Comparability Analyses**

### Estimating the Propensity Score

Next, a linear-logistic model for the conditional probability of treatment,  $Pr(A_i=a|L_i)$ , where  $L_i$  is a vector of measured confounders of the exposure and the outcome, as well as risk factors for the outcome, will be fit (Brookhart et al, 2006). The conditional probability of treatment given a set of covariates is commonly referred to as the propensity score (PS).

For the first set of comparability analyses, overlap of the propensity score across treatment groups will be evaluated. Non-overlap in the PS will be addressed with trimming of subjects at the extremes of the PS distribution. In addition, the mean standardized difference for all variables included in the PS model will be estimated. An absolute mean standardized difference > 0.1 for a given confounder or risk factor for the outcome will be used as a measure of potential imbalance (Austin, 2009; Austin et al. 2007). Covariates in the propensity score model with an absolute standardized difference > 0.1 will be examined for potential inclusion in the outcome model or will be used as evidence of insufficient overlap in the distribution of baseline characteristics across treatment groups. Using PS overlap and cut points for the mean standardized difference to make decisions about cohort comparability are part of an iterative process that potentially involves trimming of subjects (because of poor overlap in the PS) and accounting for confounders in the outcome model rather than the exposure model. As such, this process provides guidance on whether cohorts are comparable and contributes additional information to the body of evidence used to determine whether comparative analyses should be initiated or not.

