### Negative Control Outcome Analyses

Negative control outcome studies are designed to detect and reduce residual bias between treatment groups (Lipsitch et al, 2007, Arnold and Ercumen, 2016). Negative control outcomes are chosen that have no plausible mechanism by which they can be caused by the treatment of interest but do share unmeasured confounders (eg, lifestyle [smoking history, alcohol use], and anthropometric [BMI] variables) with the primary treatment-outcome relation. After controlling for measured confounders, any observed association between the treatment and negative control outcome can be attributed to unmeasured confounding between the groups, rather than a true causal relationship. For example, if the outcome for a comparative safety study is acute MI, the ideal negative control outcomes would share a similar confounding structure as would be hypothesized

for treatment selection (eg, erenumab-aooe vs. other mAbs targeting the CGRP pathway) and the outcome of interest (acute MI). Common outcomes used as negative controls in prior epidemiologic studies of treatments include risks of accidents or hospitalizations for trauma or injury (Dormuth et al, 2009; Brookhart et al, 2007; Jackson et al, 2006).

Selection of migraine preventive treatment is likely affected by many factors associated with a patient's prognosis that can lead to bias when comparing treatment groups in non-interventional settings. Patients initiating newer medications, such as mAbs targeting the CGRP pathway, may have more severe disease and be at higher risk for poor outcomes in comparison to patients initiating other migraine preventive therapies, such as selected SOC migraine preventive medications (anti-epileptics) or onabotulinumtoxinA . It is of interest to understand whether the incidence of clinical outcomes among patients initiating other migraine preventive medications after controlling for measured confounding factors. We will use a negative control study design to investigate this comparability of patients initiating different types of migraine preventive treatments. The results of this analysis will help inform the appropriateness of comparative safety analysis for the two CV outcomes of interest (acute MI and stroke). The negative control outcomes that may be included in the analysis are:

- o Decubitus ulcer
- o Dementia
- o Transfusions
- o Accidents
- Annual wellness visit
- Pelvic exams for cancer screening
- o Influenza vaccine use
- o Mohs surgery

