- Herpes zoster vaccine
- Colon cancer screening
- Visual field tests
- Non-skin cancers
- o Fractures

We will estimate the cumulative incidence (ie, risk) and risk ratios of negative control outcomes for each treatment group comparison, controlling for measured confounders and potential differential loss to follow-up with inverse probability weights. Null

associations between the migraine preventive treatments and the negative control outcome are hypothesized. For this component of the study, an expert panel will guide selection of the final set of negative control outcomes to be used for this study.

We will use Bayesian analyses to provide evidence of treatment group comparability. The negative control effect estimates will be included as inputs (priors) for each treatment comparison, to create a posterior distribution of the bias parameter. Based on the distribution of the bias parameter, we will then estimate the probability that the bias for treatment comparison X vs. Y is less than some threshold. We will subjectively set the threshold for the risk ratio as anything between 0.91 and 1.10 as acceptable, and the Bayesian analysis will provide the posterior probability that the level of bias (unmeasured confounding) is <10% of the null. If this probability is greater than 90% we will proceed with the comparative analysis.

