### **Gated Analyses**

### Estimating the Cumulative Distribution of a Right-Censored Counterfactual Outcome

If appropriate based on comparability analyses, a comparison of the effect of erenumabaooe versus other mAbs targeting the CGRP pathway on acute MI at t=6 months, t=1 year, and t=2 years will be undertaken, where the effect measure of interest is the RR, and the possible sources of bias are confounding and dependent censoring.

First, to address confounding, let  $A_i$  be a discrete random variable denoting exposure to erenumab-aooe (a=1) or other mAbs targeting the CGRP pathway (a=0) for patient i,

and let  $T_i^a$  be the counterfactual time from medication initiation to the acute MI outcome for patient *i*. The counterfactual cumulative incidence of the outcome is then  $R^a(t) = \Pr(T_i^a < t)$ , and the estimate of the RR is:

$$RR(t) = \frac{R^1(t)}{R^0(t)}$$

To account for confounding we will use IPTWs, which will be constructed as follows:

$$\widehat{W}_i^1 = \frac{1}{\widehat{Pr}(A_i = a | L_i)}$$

For the analyses described here,  $Pr(A_i=a|L_i)$  is the conditional probability of treatment (ie, the propensity score described previously). The set of covariates comprising  $L_i$  are listed in Appendix D. The cumulative incidence curves for acute MI, weighted by IPTWs, now account for confounding by measured covariates, but still assume that censoring occurs at random. As previously noted, the risk ratio estimates and 95% confidence intervals at six months, at one year, and at two years will be presented; however, we are also interested in the entire cumulative incidence curve over time. The cumulative incidence curve will be presented graphically.

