# Appendix D: *A Priori* List of Covariates to be Included in the Treatment and Censoring Modelsa

Footnotes defined on last page of table

Page 1 of 4

Characteristic	Treatment Model	Censoring Model	Numerical (N) or categorical (C)	Covariate assessment period*
Healthcare Utilization	Baseline period, Follow-up			
Ambulatory visits	Х	Х	N	
Emergency room visits	Х	Х	N	
Inpatient hospital visits	Х	Х	N	
Pneumococcal vaccination		Х	С	
Influenza vaccination		Х	С	
Herpes zoster vaccination		Х	С	
Eye exam		Х	С	
Screening colonoscopy		Х	С	
Screening PSA test		Х	С	
Screening fecal occult blood test		Х	С	
Screening mammogram		Х	С	
Oxygen equipment use		Х	С	
Home hospital bed		Х	С	
Mobility aids		Х	С	
Mechanical ventilation		Х	С	
Ambulance / life support		Х	С	
Rehabilitation services		Х	С	
Overall Medication Utilization	Baseline period, Follow- up			
Generic medications dispensed	X	Х	N	
Unique drug classes dispensed	Х	Х	N	

Footnotes defined on last page of table

Page 2 of 4

Characteristic	Treatment Model	Censoring Model	Numerical (N) or categorical (C)	Covariate assessment period*
Other Medications				Baseline Period
Contraceptives	Х	Х	С	
Anti-hypertensives	Х	Х	С	
Anti-coagulants	Х	Х	С	
Anti-platelets	Х	Х	С	
Lipid-lowering agents	Х	Х	С	
Anti-diabetics	Х	Х	С	
Cardiac glycosides	Х	Х	С	
Calcium gluconate	Х	Х	С	
Fludrocortisone/ Midodrine	Х	Х	С	
Weight loss prescriptions	Х	Х	С	
Fludrocortisone/ Midodrine	Х	Х	С	
Hyperpolarization-activated cyclic nucleotide-gated channel blocker	Х	X	С	
Comorbidities	I	1	1	Baseline Period
Diabetes mellitus	Х	Х	С	
Hypercholesterolemia	Х	Х	С	
Hypertension	Х	Х	С	
Liver disease / Cirrhosis	Х	Х	С	
Depression	Х	Х	С	
Chronic Obstructive Pulmonary Disease (COPD)	Х	X	С	
Renal Disease	Х	Х	С	
Cardiac arrhythmia	Х	Х	С	
Asthma	Х	Х	С	
Human immunodeficiency virus (HIV)	Х	Х	С	
Lupus	Х	Х	С	
Epilepsy/Seizure/Convulsions	Х	Х	С	
Anxiety	Х	Х	С	

Footnotes defined on last page of table

Page 3 of 4

Characteristic	Treatment Model	Censoring Model	Numerical (N) or categorical (C)	Covariate assessment period*
Comorbidities (continued)			Baseline Period	
Depression	Х	Х	С	
Peripheral Artery Disease	Х	Х	С	
Venous thromboembolism	Х	Х	С	
Critical limb ischemia	Х	Х	С	
Myocardial Ischemia	Х	Х	С	
Congestive heart failure	Х	Х	С	
Acute myocardial infarction	Х	Х	С	
Unstable angina	Х	Х	С	
Prinzmetal angina	Х	Х	С	
Other and unspecified angina pectoris	Х	Х	С	
Acute atrial fibrillation	Х	Х	С	
Paroxysmal atrial fibrillation	Х	Х	С	

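### Fourteen preventive-care and frailty markers are listed for the censoring model only, so the treatment comparison adjusts for them only indirectly and their balance is never formally checked

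*Protocol*

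**What the plan says.** In the healthcare-utilization block of Appendix D, the rows for "Ambulatory visits", emergency room visits and inpatient visits are marked for both the treatment and the censoring model. The next 14 rows are marked for the censoring model only:

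- Eight preventive-care rows: pneumococcal, influenza and herpes zoster vaccination, eye exam, colonoscopy, PSA test, fecal occult blood test, mammogram.
- Six frailty or acuity rows: oxygen equipment, home hospital bed, mobility aids, mechanical ventilation, ambulance or life support, and "Rehabilitation services".

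The two medication-count rows that follow are again marked for both models.

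Section 8.7.2.4 sets the rules. The propensity-score vector "is a vector of measured confounders of the exposure and the outcome, as well as risk factors for the outcome", and its members "are listed in Appendix D". The censoring vector is described as variables related both to leaving follow-up (drop-out, switching, discontinuation) and to the outcome. Standardized differences are to be computed for the variables in the propensity-score model.

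Under Negative Control Outcome Analyses, the protocol states that "Selection of migraine preventive treatment is likely affected by many factors associated with a patient's prognosis". It attributes a negative-control association that remains after adjustment for measured confounders to unmeasured confounding. The 13 candidate controls include "Influenza vaccine use", herpes zoster vaccine and "Colon cancer screening".

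**The concern.** If a variable is related to the outcome, as the protocol requires of a censoring covariate, its own definition of the propensity score calls for it there too. Censoring weights do not make up for the omission: they address dependent loss of follow-up and do not balance a baseline marker between treatment groups.

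Two things are at stake. First, imbalance in frailty or health-seeking that is measured, but not captured by the other covariates, would stay in the risk ratios for acute MI and stroke, and no planned balance statistic would show it. Second, the negative controls would be misread. Three candidates are follow-up counterparts of omitted baseline rows ("Influenza vaccination", for example). An association with one of them could come from a variable already listed for extraction, while the protocol would count it as evidence of unmeasured confounding.

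**Working it through.** **Step 1. Consistency of the rules.**

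| Place in the protocol | Content |
|---|---|
| 8.7.2.4, Estimating the Propensity Score | Score holds confounders and outcome risk factors |
| 8.7.2.4, Gated Analyses | Appendix D defines the members of the score |
| 8.7.2.4, Accounting for Informative Censoring | Censoring covariates are related to censoring and to the outcome |
| Appendix D | 14 rows in the censoring model, not in the treatment model |
| 8.7.2.4, Estimating the Propensity Score | Balance checked for score variables only |

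The first four lines do not fit together without a stated reason. The fifth means that the 14 rows escape the balance check.

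**Step 2. What one omitted marker could do.** The protocol has no figure to reproduce here. Section 8.9.1.4 gives the correction for an omitted dichotomous confounder; inverted, it is

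bias = [RR_CD·p1 + (1 − p1)] / [RR_CD·p0 + (1 − p0)].

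All prevalences and RR_CD values below are assumptions. They are also crude: they ignore what visit counts, medication counts and comorbidities would absorb, so the residual bias may well be smaller.

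| Assumed marker | p1 vs p0 | RR_CD | Bias | SMD |
|---|---|---|---|---|
| Common, preventive care | 40% vs 30% | 1.5 to 5 | 1.04 to 1.18 | 0.21 |
| Common, smaller gap | 35% vs 30% | 1.5 to 5 | 1.02 to 1.09 | 0.11 |
| Rare, frailty | 1% vs 0.5% | 1.5 to 8 | 1.00 to 1.03 | 0.06 |
| Less rare, frailty | 5% vs 3% | 1.5 to 8 | 1.01 to 1.12 | 0.10 |
| Frailty, wider gap | 2% vs 5% | 3 | 1.04/1.10 = 0.945 | 0.16 |
| Frailty, widest gap | 2% vs 6% | 4 | 1.06/1.18 = 0.898 | 0.21 |

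Several of these exceed the protocol's 0.1 flag for imbalance, but the flag is not applied to these rows.

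**Step 3. Effect on one negative control.** Assume baseline influenza vaccination of 35% vs 45%, with repeat vaccination in 70% of those vaccinated at baseline and 20% of the others:

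- 0.35 × 0.7 + 0.65 × 0.2 = 0.375
- 0.45 × 0.7 + 0.55 × 0.2 = 0.425
- RR = 0.375/0.425 = 0.88, becoming 1.00 once the baseline value is balanced.

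**Step 4. Effect on the decision to proceed.** The rule is a posterior probability above 90% that a pooled bias parameter lies between 0.91 and 1.10. With a normal posterior on the log scale (SDs assumed):

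| Pooled bias | SD 0.02 | SD 0.03 | SD 0.04 | SD 0.05 |
|---|---|---|---|---|
| 1.00 | 1.00 | 1.00 | 0.98 | 0.94 |
| 1.05 | 0.99 | 0.94 | 0.88 | 0.82 |
| 1.08 | 0.82 | 0.73 | 0.68 | 0.64 |

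A shift in one control is diluted by pooling. With 13 equally weighted controls (an assumption) and the other controls at 1.00, one control at 0.88 moves the pooled value to exp(ln 0.882/13) = 0.99. Three such controls move it to exp(3 × ln 0.882/13) = 0.97. Both stay inside the bounds. A smaller final set would dilute less.

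**The case against.** A reader might infer that frailty and health-seeking are wholly unadjusted, and that a single control at 0.88 would stop the comparison. The documents support neither. The treatment model contains three visit counts, two medication counts and 35 comorbidity rows, including prior stroke, TIA, MI, heart failure and COPD; rehabilitation or mobility-aid use plausibly acts on stroke risk largely through such conditions. The rule for proceeding rests on a pooled bias parameter, and an expert panel has yet to choose the controls, so influenza vaccine may never be used.

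Other objections have partial force:

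- PSA tests, mammograms and eye exams are not obvious risk factors for MI or stroke. This stands as far as it goes: the protocol's rule bears most directly on the six frailty rows, and the preventive-care rows belong as markers of health-seeking.
- Adjusting for baseline influenza vaccination pushes the influenza control toward the null by construction and may make it a weaker signal of smoking or other lifestyle differences. This stands and shapes the fix.
- The footnote to Appendix D lets variables be added, Section 8.7.2.5.3 plans a high-dimensional propensity score, and the most prevalent procedures are described by cohort. The first is optional and driven by the commonest codes, which tends to miss rare frailty markers. The second is a sensitivity analysis for the comparative stage. The third is descriptive and carries no balance criterion. None replaces entry in the main model.
- Markers such as ventilation or a home hospital bed will be rare at ages 18 to 64, so they may matter little. This also stands.

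**Conclusion.** The point holds as an unexplained inconsistency that leaves 14 measured markers only indirectly adjusted and outside the balance check, and that makes a negative-control association harder to interpret. Its size cannot be stated from the protocol, which gives no prevalences, marker-outcome associations or expected imbalance. Under the assumed inputs a single marker matters little when rare (bias 1.00 to 1.03 at 1% vs 0.5%) and could matter when common and imbalanced (1.04 to 1.18 at 40% vs 30%), always before allowing for the covariates already in the score. The decision to proceed would change only if the pooled bias moved enough: a pooled value of 1.05 passes with a posterior SD of 0.03 or less and fails at 0.04 or more. It is worth correcting because the change is cheap and removes a doubt about how the controls are read. It does not show that the comparison is biased by a known amount or that it would be stopped.

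**What to change.** In Appendix D:

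- Mark the six frailty or acuity rows for the treatment model, and mark the eight preventive-care rows as well, as health-seeking markers.
- State that only baseline-window values enter the treatment model. The block's assessment period now covers both baseline and follow-up; follow-up values should stay in the censoring model, since post-index values must not enter a propensity score.
- Include all 14 in the standardized-difference check for each of the three contrasts.

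In the negative-control section, where a chosen control repeats a baseline marker (influenza vaccine, zoster vaccine, colon cancer screening), report it with and without adjustment for that marker, or prefer other controls.

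The cost is some extra coding, because none of the 14 is among the baseline covariates in Table 1, and a negligible loss of precision with projected cohorts of about 13,000 to 23,000.

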#### Table 1. Baseline Covariates

Footnotes defined on last page of table

Page 2 of 5

Variable	Measurement	
Concomitant Medications		
Overall Medication Utilization a		
Number of unique generic medications dispensed	Continuous, and categorized based on distribution	
Number of unique drug classes dispensed	Continuous, and categorized based on distribution	
Preventive Migraine Medications		
Anti-epileptic agents	0/1 indicator at study entry for Carbamazepine, Gabapentin, Levetiracetam, Pregabalin, Topiramate, valproic acid, divalproex sodium, Zonisamide	
Anti-hypertensive, beta blockers	0/1 indicator at study entry for Atenolol, Bisoprolol, Metoprolol, Nadolol, Nebivolol, Pindolol, Propranolol, Timolol	
Anti-hypertensive, calcium channel blockers	0/1 indicator at study entry for Flunarizine, Verapamil,	
Anti-hypertensive, other	0/1 indicator at study entry for Candesartan, Clonidine, Lisinopril	
Anti-depressants, serotonin norepinephrine reuptake inhibitors	0/1 indicator at study entry for Duloxetine, Desvenlafaxine, Venlafaxine	
Anti-depressants, tri-cyclics	0/1 indicator at study entry for Amitriptyline, Desipramine, Doxepin, Imipramine, Nortriptyline, Protriptyline	
Anti-depressants, selective serotonin reuptake inhibitors	0/1 indicator at study entry for Escitalopram, Citalopram, Sertraline	
Botulinum toxin	0/1 indicator at study entry for AbobotulinumtoxinA, IncobotulinumtoxinA, OnabotulinumtoxinA, RimabotulinumtoxinB	
Other migraine preventive agents	0/1 indicator at study entry for Carisoprodol, Cyproheptadine, Guanfacine, Memantine, Methysergide, Milnacipran, Tizanidine	
Acute Migraine Medications		
Ergotamines	0/1 indicator at study entry for Dihydroergotamine mesylate, Ergotamine tartrate, Ergotamine tartrate + caffeine, Ergotamine tartrate + caffeine + belladonna + pentobarbital	
Triptans	0/1 indicator at study entry for Almotriptan, Eletriptan, Frovatriptan, Naratriptan, Rizatriptan, Sumatriptan (with and without naproxen), Zolmitriptan	

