#### Table 1. Baseline Covariates

Footnotes defined on last page of table

Page 3 of 5

Variable	Measurement	
Acute Migraine Medications (continued)		
NSAIDS	0/1 indicator at study entry for Aspirin, Celecoxib, Diclofenac, Diflunisal, Etodolac, Fenoprofen, Flurbiprofen, Ibuprofen, Indomethacin, Ketoprofen, Ketorolac, Magnesium salicylate, Meclofenamic Acid, Mefanamic Acid, Meloxicam, Nabumetone, Naproxen, Oxaprozin, Piroxicam, Rofecoxib, Salsalate, Sulindac, Tolmetin, Valdecoxib	
Opioids	0/1 indicator at study entry for Codeine, Fentanyl, Hydrocodone, Hydromorphone, Morphine Sulfate, Oxycodone, Oxymorphone, Tramadol, Alfentanil, Buprenorphine, Butorphanol tartrate, Dezocine, Dihydrocodeine, Levomethadyl, Levorphanol, Meperidine, Methadone, Nalbuphine, Opium / belladonna alkaloids / opium alkaloids, Pentazocine, Propoxyphene, Remifentanil, Sufentanil, Tapentadol	
NonNSAID NonOpioid Analgesics	0/1 indicator at study entry for Acetaminophen, Baclofen, Butalbital, Ziconotide	
Other acute migraine treatment	0/1 indicator at study entry for Lasmiditan	
Other Medications		
Contraceptives	0/1 indicator at study entry	
Anti-hypertensives		
Aldosterone antagonist	0/1 indicator at study entry	
Angiotensin receptor blockers	0/1 indicator at study entry	
Angiotensin-converting enzyme (ACE) inhibitors	0/1 indicator at study entry	
Beta-blockers	0/1 indicator at study entry	
Calcium-channel blockers	0/1 indicator at study entry	
Diuretics	0/1 indicator at study entry	
Other anti-hypertensives	0/1 indicator at study entry	
Anti-coagulants	0/1 indicator at study entry	
Anti-platelets	0/1 indicator at study entry	
Lipid-lowering agents		
Statins	0/1 indicator at study entry	
Non-statins	0/1 indicator at study entry	

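### Appendix D gives the propensity score one antihypertensive line where Table 1 has class indicators, so weighting can unbalance cardiovascular antihypertensive use without the balance check showing it

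*Protocol*

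**What the plan says.** Protocol Section 8.7.2.4, under the counterfactual cumulative-incidence heading, states that the covariates in the treatment model are "listed in Appendix D". That appendix has one row, "Anti-hypertensives", marked for both the treatment and the censoring model and coded C (categorical). Its block of migraine preventives has rows for Any MPT, antidepressants, anti-epileptics, botulinum toxins and other agents. It has none for antihypertensives.

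Table 1 in Section 8.3.3 is finer. Among the preventive medications it has "Anti-hypertensive, beta blockers", "Anti-hypertensive, calcium channel blockers" and a third row defined as "0/1 indicator at study entry for Candesartan, Clonidine, Lisinopril". Under other medications it has seven antihypertensive classes, among them "Angiotensin receptor blockers" and "Angiotensin-converting enzyme (ACE) inhibitors". It also separates statins from non-statins and insulin from non-insulin. Appendix D has one row for lipid-lowering agents and one for anti-diabetics.

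On balance, Section 8.7.2.4 says that "the mean standardized difference for all variables included in the PS model will be estimated". The paragraph on the decision to proceed applies its 0.10 threshold to the same set of variables.

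**The concern.** Section 6.1 lists antihypertensives among the prophylactic options for migraine. Section 8.2.2 says guidelines expect two standard preventives to have failed before erenumab is started. A positive antihypertensive indicator may therefore mean migraine prevention more often in the erenumab arm, and treated hypertension more often among users of anti-epileptics or onabotulinumtoxinA.

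If so, making the combined indicator equal across arms does not make its components equal. A component that was balanced before weighting can be pushed out of balance. The component that matters for acute MI and stroke is the cardiovascular one. The combined row would still show a standardized difference near zero, and no other row in the balance table would show the problem directly.

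**Working it through.** The protocol states no figure on this point, so there is none to reproduce. It also gives no prevalences, so every percentage below is an assumption.

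**Inputs.** T is use of an ACE inhibitor, ARB or diuretic: 12% in both arms. M is beta-blocker use for migraine: 18% erenumab, 6% comparator, independent of T. A is T or M, the combined row. Arms are equal in size. T multiplies outcome risk by k = 2 or 3, and M has no effect. The true risk ratio (RR) is 1.00, and T is balanced before weighting.

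**Step 1: combined row alone.**
- P(A), erenumab: 1 − 0.82 × 0.88 = 0.2784.
- P(A), comparator: 1 − 0.94 × 0.88 = 0.1728.
- Mean of the two: 0.2256.
- With one binary covariate, inverse-probability weighting sets P(A) to 0.2256 in each arm and leaves P(T|A) unchanged. Weighted T is 0.2256 × 0.12/0.2784 = 0.0972 for erenumab and 0.2256 × 0.12/0.1728 = 0.1567 for the comparator.
- SMD = (0.0972 − 0.1567)/√[(0.0972 × 0.9028 + 0.1567 × 0.8433)/2] = −0.0595/0.3316 = −0.18.
- RR = [1 + (k−1) × 0.0972]/[1 + (k−1) × 0.1567], which is 1.0972/1.1567 = 0.95 for k = 2 and 1.1944/1.3134 = 0.91 for k = 3.

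**Step 2: add the other relevant Appendix D rows.** This uses exact cell probabilities, a main-effects logistic propensity score and weights 1/Pr(A_i = a | L_i). The hypertension diagnosis is coded in 50% to 90% of T users and in 8% of others. Any MPT is taken to include M, and other preventives are set at 70% versus 50%.

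| Terms in the model | Weighted T, erenumab vs comparator | SMD of T | RR (k = 2 to 3) |
|---|---|---|---|
| Combined row + diagnosis | 9.9–10.4% vs 15.3–14.4% | −0.16 to −0.12 | 0.92–0.97 |
| Also Any MPT and other preventives | 10.3–10.6% vs 14.3–13.7% | −0.121 to −0.095 | 0.94–0.97 |
| T and M as separate terms, with diagnosis and other preventives | 12.0% vs 12.0% | 0.00 | 1.00 |

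In the first two models every variable in the model has an absolute SMD of 0.005 or less, so the balance table would look clean.

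**Step 3: vary the assumption that drives the result** (combined row + diagnosis).
- M 10% vs 8%: SMD −0.02 to −0.03.
- M equal in both arms: SMD 0.00, RR 1.00.
- M 6% vs 18% (arms reversed): SMD +0.12 to +0.16, RR 1.04 to 1.09.

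**Step 4: a second set of assumptions.** Hypertension diagnosis is 15–35% in both arms, 50–70% of those diagnosed are treated, and preventive antihypertensive use is 30–45% versus 15–20%. With diagnosis, Any MPT and other preventives in the model, the SMD of treated hypertension runs from −0.03 to −0.17. The small end (−0.03 to −0.04) belongs to 30% versus 20%. With diagnosis 25%, 70% treated and preventive use 45% versus 15%, treatment is 15.4% versus 19.6% (SMD −0.11), while the combined row, diagnosis and Any MPT are all below 0.01.

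**The case against.** **The coding is open.** The row is coded C, as are five-level age and region, and its label is also a Table 1 group heading. It might stand for the classes beneath it. That is possible, but nothing in the protocol says so. Since the protocol itself fixes the list, the mapping should be explicit.

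**Other rows help.** Any MPT may include preventive antihypertensives, and the model also has the hypertension diagnosis and counts of medications and drug classes. This stands in part. Any MPT and the diagnosis shrink the effect in the calculation without removing it, and Any MPT is not defined. The counts were not modelled.

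**Other analyses help.** The Appendix D footnote permits further variables, and Section 8.7.2.5.3 plans a high-dimensional propensity score that draws on drug class. The first is optional and the second is a sensitivity analysis, so neither secures the main result.

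**The bias is tolerable.** An RR of 0.92 to 0.97 lies inside the 0.91 to 1.10 band that the protocol accepts for residual bias, and detectable stroke ratios are 1.41 to 1.58. This stands as a limit on importance, since the bias alone would rarely change a conclusion. It remains avoidable bias, and the negative controls are not aimed at antihypertensive treatment.

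**A stronger reading.** A reader might infer that the adjustment will hide harm from erenumab in every contrast. The documents do not support that. Direction depends on prevalences they do not give, and the prior-failure argument does not separate erenumab from the other CGRP antibodies.

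**Conclusion.** The point holds as a weakness in how the adjustment set is specified, for the contrasts with anti-epileptics and onabotulinumtoxinA. Appendix D is coarser than Table 1 on a treatment that marks cardiovascular risk and is also used for migraine. The balance criterion cannot detect an imbalance that weighting on the combined row creates.

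The size is conditional. At 18% versus 6% beta-blocker use it is a hidden SMD of about 0.10 to 0.16 and a bias of about 3% to 8% in the risk ratio. It is near zero if preventive use is similar and of opposite sign if the arms are reversed. Nothing in the protocol says which case applies.

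A reader might extend the argument to the merged lipid-lowering and anti-diabetic rows and attach a size to it. The documents give no basis for that. Those rows raise only ordinary coarse adjustment, and no magnitude is claimed.

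**What to change.** In Appendix D, replace the single antihypertensive line by the Table 1 class indicators: beta blockers, calcium-channel blockers, ACE inhibitors, ARBs, diuretics, aldosterone antagonists and other. Enter each class once. Table 1 lists beta blockers and calcium-channel blockers both as preventives and as antihypertensives, so copying both sets would create overlapping terms. Include each class in the balance table and in the decision to proceed. Define Any MPT. Carry over the statin/non-statin and insulin/non-insulin rows as finer adjustment.

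The cost is a few more propensity-score terms, using variables Table 1 already defines, in cohorts projected at about 13,000 to 23,000. Claims do not record indication, so the gain is balance by drug class and not a clean split between migraine and cardiovascular use.
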